6. Bone marrow aspiration on day 28 (± 7 days), then every 2 cycles (± 1 cycle) for 6 cycles, then every 3 months; then as clinically indicated. Bone marrow aspirations to be performed at MDACC.
7. Flow cytometry for MRD (peripheral blood and/or bone marrow) every 2 cycles (± 1 cycle) for 6 cycles, then every 3 months; then as clinically indicated.
8. Correlative studies (Appendix C). Every effort will be made to collect all samples at all-time points for all patients; however, missing collection in one or more of these time points in occasional patients will not be considered a protocol deviation/violation.
9. Patients who complete therapy will be followed as clinically indicated after the end of therapy. If treatment is resumed follow-up will be done according to the follow-up schedule that was being done at the time they discontinued therapy.

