9.0 STATISTICAL CONSIDERATIONS

This is a phase II study of Nivolumumab as a maintenance therapy in patients with high risk AML and in first or second remission. The primary objective is to assess the recurrence-free survival rate at 6 months. It is expected the median RFS under the treatment is at least 8 months. Assume that RFS time follows an exponential distribution, the RFS rate at 6 months will be 59.5%. A maximum of 30 patients will be enrolled, and the study will monitor both futility and toxicity.

Futility monitoring

The study will be continuously monitoring RFS for futility, using the method of Thall, Wooten, and Tannir (2005). It is assumed that the RFS time is exponentially distributed with a median of λ_E among patients who receive nivolumumab as a maintenance therapy, and a median of λ_H is assumed for the historical treatment. Further, we assume that λ_H follows an inverse gamma distribution, i.e., $\lambda_H \sim IG(3.6, 20.8)$, which has a mean of 8 months and variance of 40. To reflect the little prior knowledge of λ_E we assume an inverse gamma prior distribution with the same mean of 8 months and a much larger variance of 500, i.e., $\lambda_E \sim IG(2.128, 9.024)$. The trial will be stopped early if $Pr(\lambda_E > \lambda_H | \text{data}) < pL$, where $pL=0.25$. That is, the study will be stopped if at any time during the study the data suggest that there is less than 25% probability that the median RFS was

longer than that in the historical data. This futility monitoring rule will be first applied when 10 patients have been enrolled. A maximum of 30 patients will be enrolled into this study at an expected accrual rate of 2-3 patients per month. From historical experience, 25% of patients in this cohort may become eligible for stem cell transplant and may come off study. For purposes of this analysis, these patients will be censored at the time of receiving transplant. Patients will be followed up for an additional 6 months after completing treatment on protocol. Once these patients come off of study, they will be followed on a leukemia department long-term follow-up protocol and will not be receiving the evaluations described in section 6.2. The trial will be conducted using the Clinical Trial Conduct (CTC) website maintained by the Department of Biostatistics at MDACC. The website will be programmed with the operating characteristics of the Bayesian design of this protocol to allow continuous monitoring for futility.

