The operating characteristics of the design, based on an overall assumed accrual rate of 2.5 patients per month and an additional follow-up of 6 months with 5000 simulated trials per scenario, are given in the following table. OneArmTTE (version 2.2) was used for the design and simulation.

Scenario	True Median (months)	True RFS rate at 6 months	Pr(Stopped Early)	Mean No. patients (25%, 75%)	Average Trial Duration (months)
1	2	12.50%	1	10.5 (10, 10)	4.24
2	4	35.40%	0.86	16.7 (10, 23)	7.83
3	6	50%	0.36	24.1 (14, 30)	13.56
4	8	59.50%	0.16	27.2 (30, 30)	16.01
5	10	66%	0.08	28.6 (30, 30)	16.98
6	12	70.70%	0.04	29.2 (30, 30)	17.4

Toxicity monitoring

In addition, we will continuously monitor treatment-related toxicities using the Bayesian approach of Thall, Simon, Estey (1995). Specifically, the trial will be stopped if $\text{Prob}(\pi_T > 0.30 | \text{data}) > 0.88$, where π_T is the toxicity rate and we assume a beta (0.6, 1.4) prior for π_T . That is, if at any given time, there is more than 88% probability that the toxicity rate of the maintenance therapy with nivolumab is greater than 30%, the trial will be stopped. For the purpose of toxicity monitoring, toxicities are defined as any treatment –related clinically significant \geq grade 3 non-hematologic AEs occurred any time during the trial. We will apply this stopping rule starting from the 10th patient. The stopping boundaries corresponding to this toxicity monitoring rule are described in the following table:

Stopping boundaries for treatment-related grade 3, 4 non-hematologic toxicities

The number of patients evaluated for toxicities	10 -12	13-15	16-18	19-20	21-23	24-26	27-29
Stop the trial if greater than or equal to this many of patients with toxicities	6	7	8	9	10	11	12

The operating characteristics for toxicity monitoring are described in the following table. MultcLean Desktop 2.1.0 was used for the design and simulations for toxicity monitoring.

Operating characteristics for Toxicity Monitoring

True Toxicity Rate	Early Stopping Probability	Sample Size		
		25 th percentile	Median	75 th percentile
0.1	0.0007	30	30	30
0.2	0.0353	30	30	30
0.3	0.2447	29	30	30
0.4	0.635	11	18	30
0.5	0.9134	10	11	15

A toxicity summary will be submitted to the IND medical monitor after every 3 patients starting from the 10th patient.

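### The futility table matches relapse known on the day it occurs; on the planned marrow and blood-count schedule the 0.86 chance of stopping at a 4-month median may be lower, and the plan omits the follow-up rule that decides how much

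*Combined protocol and SAP*

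**What the plan says.** Section 9.0 (Futility monitoring) states "The study will be continuously monitoring RFS for futility" and "It is assumed that the RFS time is exponentially distributed". The historical median has an inverse gamma prior "which has a mean of 8 months and variance of 40". For the nivolumab median, "we assume an inverse gamma prior distribution with the same mean of 8 months and a much larger variance of 500". The trial stops when there is "less than 25% probability that the median RFS was" longer than in the historical data. "This futility monitoring rule will be first applied when 10 patients have been enrolled"; the maximum is 30.

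The operating characteristics are "based on an overall assumed accrual rate of 2.5 patients per month and an additional follow-up of 6 months", with 5000 simulated trials per scenario. At a true median of 4 months the table prints a stopping probability of 0.86 and a mean of 16.7 patients. At 6 and 8 months it prints 0.36 and 0.16.

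Section 6.2 item 6 sets the marrow schedule: "Bone marrow aspiration on day 28 (± 7 days), then every 2 cycles (± 1 cycle) for 6 cycles", then every 3 months. A cycle is 4 weeks (section 4.2.1). Item 3 sets CBC with differential weekly in cycle 1, every 2 weeks for two cycles, then every 4 weeks. Section 7.0 allows relapse to be declared from marrow, from blood blasts above 10%, or from extramedullary disease. Where a repeat marrow is needed, it dates relapse at the first marrow in which more than 5% blasts were seen.

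Section 9.0 gives no detection delay. It does not say how follow-up is counted between assessments, or whether the scenario median refers to actual or recorded relapse.

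**The concern.** The rule uses two quantities at each look: the number of relapses and the total event-free time. A patient who has relapsed but has not yet been found to have relapsed supplies no event. If follow-up is counted to the look date, that patient also supplies event-free time after the relapse. Both errors make the drug look better than it is at that moment. They weigh most on recently enrolled patients, who dominate the early looks.

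This is the plan's only formal efficacy decision rule; the primary analysis is a Kaplan-Meier estimate with a confidence interval, and this point does not touch it. If the table overstates how often the rule stops, more patients are enrolled under a poor treatment than the plan implies. The delay also lowers stopping when the treatment performs as expected, so the effect is not all in one direction.

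**Working it through.** **Inputs (section 9.0).** Historical median IG(3.6, 20.8): mean 20.8/2.6 = 8, variance 8²/1.6 = 40. Nivolumab median IG(2.128, 9.024): mean 9.024/1.128 = 8, variance 8²/0.128 = 500. Both match the text. The cutoff is 0.25, the first look is at 10 patients, the maximum is 30, accrual is 2.5 per month, and there are 6 months of extra follow-up.

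**Rule.** With d relapses and total follow-up T months, the nivolumab median has posterior IG(2.128 + d, 9.024 + ln2·T). Put b = 9.024 + ln2·T. The probability that it exceeds the historical median is the Beta(2.128 + d, 3.6) distribution function at b/(b + 20.8). Setting this to 0.25 gives the boundary: stop if T is below 14.38 with 3 relapses, 20.74 with 4, or 27.13 with 5.

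**Why delay matters at the first look.** With evenly spaced accrual, the 10 patients have 0, 0.4, ..., 3.6 months of follow-up, a total of 0.4 × 45 = 18 months. Four known relapses always stop the trial, because T ≤ 18 < 20.74. If one of the four is still undetected, the trial stops only if T is below 14.38. The second marrow is due at week 12 (84 days, about 2.8 months). Three of the ten would have reached it under even spacing, or about 2.5 on average with random arrivals.

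**Reproducing the table.** The simulation used random accrual, a look at each enrolment from the tenth, one final look, relapse known at once, and 5000 trials per scenario:

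| True median (months) | 2 | 4 | 6 | 8 | 10 | 12 |
|---|---|---|---|---|---|---|
| Printed Pr(stop) | 1 | 0.86 | 0.36 | 0.16 | 0.08 | 0.04 |
| Simulated | 1.000 | 0.864 | 0.385 | 0.164 | 0.086 | 0.046 |
| Printed mean N | 10.5 | 16.7 | 24.1 | 27.2 | 28.6 | 29.2 |
| Simulated mean N | 10.7 | 16.9 | 23.8 | 27.1 | 28.4 | 29.1 |

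The 6-month row is 0.368-0.382 with other seeds and 0.369 if looks are made at the next enrolment. Monte Carlo standard error is about 0.005-0.007.

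**Adding the section 6.2 schedule.** Here the true median is time to actual relapse, relapses are dated at detection, and assessments fall on nominal days. Ranges reflect repeat runs and the way the later marrows are spaced.

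| Relapse becomes known | Others counted event-free to | Pr(stop), 4 months | Mean N, 4 months | Pr(stop), 8 months |
|---|---|---|---|---|
| At once | look date | 0.86 | 16.9 | 0.16 |
| Next scheduled CBC | look date | 0.76-0.77 | about 19 | about 0.11 |
| Next scheduled CBC | last assessment | 0.80-0.81 | about 18 | about 0.14 |
| Marrow only | look date | 0.49-0.52 | about 24 | about 0.04 |
| Marrow only | last marrow | 0.68-0.69 | about 20 | about 0.12 |

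Between the extremes, with follow-up to the look date, if 25%, 50% or 75% of relapses wait for marrow and the rest are known at once, stopping at 4 months is 0.798, 0.719 or 0.623.

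**Sensitivity (marrow only, look date, 4 months).** Accrual of 2 or 3 per month gives 0.542 or 0.496. With 25% censored at transplant (timing assumed uniform over 6 months) it is 0.525, against 0.847 with immediate knowledge.

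**If the scenario median is recorded RFS.** With CBC detection and a recorded 4-month median (onset median 3.75), stopping is 0.839 to the look date and 0.870 to the last assessment. Matching recorded 6-month RFS to 35.4% instead (onset median 3.7) gives 0.848 and 0.870, with mean N of 17.9 and 16.7. With marrow-only detection and a recorded 4-month median (onset median 3.38), it is 0.771 to the look date and 0.876 to the last marrow.

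**The case against.** A reader might infer that the table holds only under immediate knowledge of relapse, and that 0.86 is therefore not delivered. The documents do not support that, for three reasons.

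- Surveillance is not marrow alone. CBC with differential is more frequent, and blood blasts or extramedullary disease can define relapse. The share of relapses first seen in blood is not given, so 0.49 is a worst case and not an estimate.
- RFS in a trial is recorded RFS, and the historical comparator was presumably dated at detection too. On that reading with CBC detection, the printed figure is met.
- The plan does not say that undetected patients count to the look date. In the marrow-only case that choice alone moves stopping from about 0.49 to 0.68.

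All three stand, and they limit the size and certainty of the point. They do not remove it. The table's column is labelled as a true median, and on that scale every detection-dated schedule tried gives less than 0.86, including the most favourable CBC case. The answer also turns on a counting rule and a definition that section 9.0 leaves open.

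**Conclusion.** The concern holds in a limited form. The printed futility table corresponds to relapse known at once, which section 6.2 does not provide. With the true median taken as time to actual relapse and relapses dated at detection, the 0.86 at 4 months (half the historical prior mean of 8 months) becomes about 0.77-0.80 if every relapse shows on the next CBC. Under marrow-only detection it becomes about 0.49 (follow-up to the look date) to 0.68 (to the last marrow). Mean enrolment rises from 16.7 to about 18-19 or 20-24 respectively. At 8 months, stopping falls from 0.16 to between 0.04 and 0.14: fewer stops when the drug is poor, and also fewer when it performs as expected. If the scenario median means recorded RFS with CBC detection, stopping is about 0.84-0.88 and the table stands.

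These figures assume exponential RFS and assessments on nominal days; the ± 1 cycle marrow window is not modelled. The primary Kaplan-Meier analysis is outside this point.

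**What to change.** In section 9.0:

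1. State that in the monitoring calculation, event-free follow-up is counted only to each patient's last disease assessment (marrow or CBC) showing remission, not to the look date.
2. State whether the scenario median is time to actual relapse or recorded RFS.
3. Re-run the simulation with relapse revealed on the section 6.2 marrow and CBC dates, and replace the table. Because the share of relapses first seen in blood is unknown, show both the CBC and marrow-only extremes.

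Keep the section 7.0 relapse dating. Do not add a rule placing relapse midway between assessments. It would give a patient one relapse date for monitoring and another for the primary analysis. It can also over-stop: 0.23 against the printed 0.16 at 8 months, if relapse shows in blood on average 1 month after onset (an assumption).

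The cost is one simulation rerun, a short addition to section 9.0 and a data-entry rule for the monitoring website. On the actual-relapse scale, counting to the last assessment recovers only part of the gap (0.80 with CBC detection, 0.68 with marrow only), so some stated stopping probabilities will become less favourable.

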1.0 OBJECTIVES

1.1 Primary Objectives:

1. To evaluate the anti-leukemic effects of Nivolumab in patients with Acute Myeloid Leukemia (AML) who have achieved a 1st complete remission (CR) after induction chemotherapy and consolidation chemotherapy and have high risk for relapse, or have achieved a 2nd CR. The primary endpoint is defined as recurrence-free survival (RFS) rate at 6 months.

1.2 Secondary Objectives:

1. To evaluate the immunologic responses to Nivolumab among patients with AML in CR status post standard chemotherapy
2. To determine whether response to Nivolumab correlate with immunologic responses.
3. To evaluate assessment of Minimal Residual Disease (MRD) by flow cytometry as a predictor of response to immune therapy in treatment of AML and changes during the course of therapy with nivolumab
4. To evaluate time to relapse and overall survival
5. To evaluate the toxicity profile of Nivolumab among patients with AML in CR

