7.0 CRITERIA FOR RESPONSE

The primary endpoint of this study is the rate of sustained remission at 6 months from the start of study treatment.

Response criteria will be modified from the International Working Group for AML (JCO 2003; 21: 4642-9). Responders are patients who obtain a CR, CRi, or PR, with or without cytogenetic response, hematologic improvements, and morphologic leukemia-free state. Briefly, criteria are as follows:

Complete Remission (CR):

- ◆ **Peripheral blood counts:**

Neutrophil count $\geq 1.0 \times 10^9/L$
Platelet count $\geq 100 \times 10^9/L$

- ◆ **Bone marrow aspirate and biopsy:**

$\leq 5\%$ blasts
No Auer rods
No extramedullary leukemia

Complete remission with incomplete blood count recovery (CRi):

- ◆ **Peripheral blood counts:**

Neutrophil count $< 1.0 \times 10^9/L$, or
Platelet count $< 100 \times 10^9/L$

- ◆ **Bone marrow aspirate and biopsy:**

$\leq 5\%$ blasts
No Auer rods
No extramedullary leukemia

Partial Remission (PR):

- ◆ All CR criteria if abnormal before treatment except:
- ◆ $\geq 50\%$ reduction in bone marrow blast but still $> 5\%$

Morphologic Leukemia-Free State (MLF):

- ◆ Bone marrow: $\leq 5\%$ myeloblasts

Hematologic Improvement (HI): Hematologic response must be described by the number of positively affected cell lines.

- ◆ **Erythroid response (E)** (pretreatment Hgb <11 g/dL):
 - Hgb increase by ≥ 1.5 g/dL
- ◆ **Platelet response (P)** (pretreatment platelets $<100 \times 10^9/L$):
 - Absolute increase of $\geq 30 \times 10^9/L$ for patients starting with $>20 \times 10^9/L$ platelets, or
 - Increase from $< 20 \times 10^9/L$ to $> 20 \times 10^9/L$ and by at least 100%
- ◆ **Neutrophil response (N)** (pretreatment ANC $<1.0 \times 10^9/L$)
 - At least 100% increase and an absolute increase $>0.5 \times 10^9/L$
- ◆ **Blast response (B):**
 - At least 50% reduction in blast percentage.

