For the primary analysis of the efficacy endpoint, we will use Kaplan-Meier methodology to compute the RFS rate at 6 months and the 95% confidence interval. As a secondary analysis, we will perform a competing risk analysis treating stem cell transplant as a competing event for RFS." . The Kaplan-Meier method will be used to estimate the median RFS time and the probability of overall survival. Expressions of immune mediated markers will be summarized with descriptive statistics: means medians, ranges, and standard deviations. Two-sample t test or Wilcoxon rank sum test will be used to compare the expressions of markers between patients remaining in CR and patients having recurrence disease. Scatterplots will be used to explore possible associations between clinical responses and the immunomodulatory markers. Spearman correlation coefficients will be computed to evaluate the association between MRD and immunomodulatory markers, as well as the association between MRD and the changes in marker expressions pre and post treatment.

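### Section 9.0 plans no analysis of MRD against relapse or over time, so secondary objective 3 is unanswered; the marker-by-relapse test also names no sample or status date and discards relapse times

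*Combined protocol and SAP*

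**What the plan says.** Secondary objective 3 (section 1.2) has two parts. The first is to assess "Minimal Residual Disease (MRD) by flow cytometry as a predictor of response to immune therapy"; the second is its "changes during the course of therapy with nivolumab". The data for both are scheduled: flow-cytometry MRD at baseline (section 6.1, item 8), then every 2 cycles for 6 cycles and every 3 months after that (section 6.2, item 7).

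In section 9.0, MRD enters the analysis in one sentence: "Spearman correlation coefficients will be computed to evaluate the association between MRD and immunomodulatory markers". The rest of that sentence correlates MRD with pre-to-post change in the markers. The change there is in the marker, not in MRD.

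For the immune markers and outcome (objective 2), section 9.0 plans a two-sample t or Wilcoxon rank sum test to "compare the expressions of markers between patients remaining in CR and patients having recurrence disease", plus scatterplots. The same section treats RFS as a censored time, with Kaplan-Meier estimation, and says of transplant recipients that "these patients will be censored at the time of receiving transplant".

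**The concern.** A listed objective should have at least one analysis that could answer it. If section 9.0 is followed exactly, neither part of objective 3 is addressed: a correlation between MRD and an immune marker says nothing about whether MRD-positive patients relapse sooner, and nothing about the course of MRD on nivolumab. An analysis chosen after the data are seen would then fill the gap.

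The marker test raises a smaller issue. It reduces a censored relapse time to two groups without saying when group membership is fixed or which marker sample is compared. Section 7.0 ties the primary endpoint to a date ("The primary endpoint of this study is the rate of sustained remission at 6 months from the start of study treatment"), but the test sentence does not refer to it. Patients enter over about a year and so have unequal follow-up. A patient who relapses in month 2 counts the same as one who relapses in month 14, and a patient in remission after 6 months counts the same as one in remission after 18.

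**Working it through.** **1. Objective 3 against the stated analyses**

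| Part of objective 3 | Data scheduled | Analysis in section 9.0 |
|---|---|---|
| MRD as predictor of response | Baseline MRD; RFS | None; MRD is related only to immune markers and their changes |
| MRD change during therapy | Serial MRD | None; the only change analysed is in the markers |

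The scatterplots do not help, because they set clinical response against the immunomodulatory markers, which the Spearman sentence names separately from MRD.

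**2. The plan's own figure**

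With exponential RFS and a median of 8 months (section 9.0), the hazard is ln 2/8 = 0.0866 per month. S(6) = exp(-0.0866 × 6) = 0.5946, which reproduces the stated 59.5%.

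**3. Why the status date matters**

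Inputs: 30 patients and the design simulation's setting, "based on an overall assumed accrual rate of 2.5 patients per month and an additional follow-up of 6 months". Accrual takes 30/2.5 = 12 months, so follow-up runs from about 6 to 18 months. Before transplant censoring:

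- Status fixed at month 6: 30 × (1 - 0.5946) = 12.2 recurrences.
- Status at end of follow-up: mean S = (0.5946 - 0.2102)/(0.0866 × 12) = 0.370, giving 30 × 0.630 = 18.9 recurrences.
- Share of the later group still in remission at month 6: (18.9 - 12.2)/18.9, about 36%.

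**4. Power of the group test against a Cox model (simulated)**

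Assumptions that the documents do not give: a standard-normal baseline marker with a constant log hazard ratio per SD, and transplant in 25% of patients, uniform over months 1 to 6 (section 9.0 says only that 25% may become eligible). There are about 16 RFS events. Both tests are calibrated to two-sided 5%; ranges are over repeated runs.

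| Hazard ratio per SD | Wilcoxon by status | Cox |
|---|---|---|
| 1.5 | 23–26% | 29–33% |
| 2.0 | 53–57% | 70–71% |
| 2.5 | 73–77% | 88–90% |

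Section 9.0 also says "Patients will be followed up for an additional 6 months after completing treatment on protocol". Giving every non-transplanted patient 12 months changes the hazard ratio 2 row to 57% against 72%. Applying the futility rule gives 48% against 60%. If the marker acts only after month 6, the gain disappears (11% against 11%).

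**5. What an MRD analysis could deliver**

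For a yes/no covariate with prevalence p and D events, SE(log HR) is about 1/√(D·p(1-p)). With D = 16 and a true hazard ratio of 3 (assumed):

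- p = 0.5: SE = 0.50, 95% CI about 1.1 to 8.0.
- p = 0.3: SE = 0.55, 95% CI about 1.0 to 8.7.

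Simulated power is about 56–58%. For the visit table, expected patients event-free and untransplanted are 30 × S(t) × (1 - 0.25 × (t - 1)/5). At the ends of cycles 2, 4 and 6 (t = 1.84, 3.68 and 5.52 months):

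- 30 × 0.853 × 0.958, about 25
- 30 × 0.727 × 0.866, about 19
- 30 × 0.620 × 0.774, about 14

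**6. Selection through eligibility**

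Inclusion criterion 2a admits an MRD-negative first-remission patient only with another high-risk feature. Suppose MRD truly doubles the hazard, the other feature multiplies it by h, and 40% of MRD-positive patients also carry that feature (all assumed). The initial hazard ratio among eligible first-remission patients is 2 × (0.6 + 0.4h)/h: 1.6, 1.4 and 1.2 for h = 1.5, 2 and 3. A real association can therefore be pulled toward 1.

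**The case against.** The strongest reply is that these are secondary, exploratory analyses in at most 30 patients. Objective 2 asks only whether response correlates with immunologic response, and a group test with scatterplots meets that. Section 2.6 plans a randomized trial to confirm any signal. Cox regression on about 16 events needs a proportional-hazards assumption that can barely be checked. This is largely right: it sets the severity low and is a reason to keep the planned test as a description. It does not answer the objective 3 gap, where no analysis is stated at all.

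Four stronger readings are tempting, and the documents do not support them.

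- A reader might infer that the marker test is invalid. For a baseline or fixed-time sample, with censoring unrelated to the marker, it is valid. What it loses is power, and only when the effect is roughly proportional over time.
- A reader might infer that the last available sample will be compared, so that relapsed patients are sampled earlier and any drift with time looks like an effect. Simulated false-positive rates under an assumed drift of 0.1–0.2 SD per month ran from 6% to 33%, depending on follow-up and on when sampling stops. But nothing in section 9.0 proposes that sample, and Appendix C and the companion protocol, which may set collection times, are not in the supplied text.
- A reader might infer that the unstated group for transplanted patients distorts the result. If transplant is unrelated to the marker, counting them as non-relapsed or excluding them gave 57% and 56% power at a hazard ratio of 2. A clarifying phrase is enough.
- A reader might infer that relating baseline MRD to RFS would show whether MRD predicts benefit from nivolumab. The study has one arm (section 4.1), so prognosis and prediction of benefit cannot be separated.

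**Conclusion.** The concern holds as a cheap improvement that the sponsor could make. The objective 3 gap rests on the text alone: followed as written, section 9.0 relates MRD to neither relapse nor time, although the measurements are scheduled. The marker-test point is one of missing specification and lost efficiency, not of validity. The power difference of roughly 15 percentage points at a hazard ratio of 2 per SD depends on assumed effect size, proportional hazards, and the assumed timing and share of transplant, and it vanishes for a purely late effect. Even the better analysis would be imprecise. The 6-month RFS estimate, the futility rule and the toxicity rule do not depend on any of this.

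**What to change.** In section 9.0:

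- (a) Relate baseline MRD to RFS with a single-covariate Cox model, using the transplant censoring already stated, and report the hazard ratio with its 95% CI.
- (b) Tabulate the proportion MRD-negative and the change from baseline at each scheduled assessment, with CIs and the number assessed.
- (c) Analyse each baseline immune marker against RFS with the same model. Keep the t/Wilcoxon test, scatterplots and Spearman correlations as descriptive, and name the sample and the status date for the group test.
- (d) For on-treatment markers and MRD, use a landmark at the sample date or a time-dependent covariate. Do not enter a last-available sample as a fixed covariate.

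Label all of this exploratory and unadjusted for multiplicity. Present baseline MRD as an association only, and describe it also by eligibility route: first remission by MRD, first remission by other high-risk features, second remission. On-treatment MRD is likewise an association only, because its recurrence can change treatment (section 4.2.3).

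The cost is a few sentences and a few lines of code, with no new visits or patients. The downside is a proportional-hazards assumption on about 16 events and wide intervals: at a true hazard ratio of 2 per SD, the simulated 95% CI is about 1.1 to 3.6. Correlative samples are optional, so marker analyses may have fewer than 30 patients.
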